5.1 Participants

In total, 40 subjects will be recruited aged 65+. Inclusion criterion include being able to independently stand upright > 5 min. Exclusion criteria are: (a) history of neurological disorders; (b) balance impairments (i.e. vestibular disorders); (c) cognitive impairment (Mini Mental State Exam (MMSE) < 24); (d) visual impairment precluding following of visual targets or colour-blindness as measured with the Ishihara test for color deficiency; (e) chronic musculoskeletal (e.g. osteoarthritis, osteoporosis), cardiovascular (e.g. hypertension, peripheral vascular disease) and respiratory (e.g. chronic obstructive pulmonary disease) disease, as well as diabetes related polyneuropathy.

For this study, 40 healthy older adults will be included. Our previous fNIRS study (unpublished) revealed that our primary outcome, weight-shifting speed, improved from $0,0668 \pm 0,0255$ m/s to $0,0916 \pm 0,0350$ m/s. Based on Caljouw et al.¹⁷, we expect a training effect size of 20%, resulting in a weight-shifting speed of $0,1094 \pm 0,0418$ m/s. Applying a power of 80% and alpha of 0.05 for a repeated measures ANOVA with a within-between interaction design (within: pre vs post: between: training vs control) we calculated a total sample size of 40 participants (20 per group). Considering possible data exclusion due to fNIRS measurements, the collected fNIRS data will be monitored during recruitment, and recruit more participants if necessary.

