5.3 Experimental procedure

5.3.1 General procedures

Design

Participants will be randomly allocated to the training and control groups. The control group will not receive any form of training. Randomization will be computer-generated and blocked in groups of four to achieve optimal distribution in each training arm. The study will have a repeated measures design with two test sessions on two consecutive days.

Motor and cognitive screening

We will collect data on fall frequency, Mini-Balance Evaluation System (Mini-BESTest), and Falls Efficacy Scale. The cognitive assessment will consist of Montreal Cognitive Assessment and specific tests for visuospatial and attention.

Weight-shifting task

Before starting the weight-shifting task (WASP task), functional limits of stability (fLOS) will be assessed by asking the subject to move the Centre of Mass (CoM) as far as possible over its base of support (**Fig. 3A**) in eight different directions by pushing a virtual bar away from the center position. Mean CoM shifts will be calculated and used for personalized scaling of the WASP. Only weight-shifting in the ML direction will be tested and trained to avoid motion artefacts during fNIRS data collection, and because ML weight-shifting in particular has been linked to balance and falls^{4,5}. The WASP task (**Fig. 3B**) was developed and piloted to meet the requirements for balance training for older people in a PhD project under supervision of [name] (De Vries A, 2018). Pilot data showed that the WASP is feasible for use in older adults and can capture fluency of motion as a learning outcome.

Figure 1: (A) Functional limits of stability; (B) Weight shifting task in ST. Red ball is CoM; (C) WASP + serial subtraction in DT

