6.2 Data analysis and statistics

Calculation of the CoM data will be processed using Nexus 2.4 and customized Matlab scripts. Body movement during postural control, comprising CoM displacement, deviation of trajectory and speed will be calculated. To account for motion artefacts during fNIRS measurements, we will perform visual checks and signal processing techniques, including filtering and noise removal. A linear mixed model will analyze learning effects with training group as between-subject and pre-post-retention as within subject factor.

7 Safety

There are no permanent risks involved for the subjects participating in this study. All experiments are painless and harmless for participants. A safe and existing test infrastructure will be used and experienced researchers will conduct the experiments. Participants will be informed about the procedure and possible risks of the tests before the start of the experiment. Some of the participants may feel some fatigue during the weight shifting trials. To prevent excessive fatigue, participants will be encouraged to take breaks as needed in-between all trials. The fNIRS head cap will be cleaned/washed after each participant to ensure appropriate adherence to infection control policies. Based on a recent PhD thesis on the development and validity of the WASP task [de Vries, A (PhD thesis, March 2018)] we do not anticipate that any risks will be involved in the use of this WASP task.

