### **Primary outcome:**

For the primary behavioral outcome, weight-shifting speed in the mediolateral direction will be used. Participants will shift their weight to 80% of their stability limits within the Wasp Game. As people tend to slow down when reaching the 80% limit in order to aim for the wasp, mediolateral weight-shifting speed will be determined from the 80% limit on the right side the 80% limit on the left side and vice versa. Mediolateral weight-shifting speed will be determined and compared between the three test moments (pre, post, retention) and between the two groups (training, control) during the Wasp Game ST and DT.

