### **Main analysis:**

Primary, secondary and tertiary outcomes will be compared between training and control group and pre, post and retention test using linear mixed models. We will determine the best model based on standard fitting criteria. . We will consider cognitive and balance skills as possible covariates, depending on between group differences and determined by a blind review of the data. Post-hoc testing will be corrected for multiple testing by Bonferroni corrections.

Depending on data normality, Pearson and/or Spearman correlation analysis will be performed between neural and behavioral outcomes within groups and test moments. Bonferroni corrections for multiple testing will be applied when necessary.

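### Covariates are chosen by chance group differences and the pre-test is only an outcome level: no bias, but precision available from data already collected is given up

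*SAP*

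**What the plan says.** Protocol 5.3.1: "Participants will be randomly allocated to the training and control groups". Allocation is computer-generated in blocks of four.

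SAP, Main analysis, on covariates: "We will consider cognitive and balance skills as possible covariates, depending on between group differences and determined by a blind review of the data". The sentence names no scale, no threshold and no form of entry (main effect, or with time). Protocol 5.3.1 collects several candidates: "We will collect data on fall frequency, Mini-Balance Evaluation System (Mini-BESTest), and Falls Efficacy Scale" and "The cognitive assessment will consist of Montreal Cognitive Assessment and specific tests for visuospatial and attention".

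On the model, the SAP says "Primary, secondary and tertiary outcomes will be compared between training and control group and pre, post and retention test using linear mixed models", and Protocol 6.2 says "A linear mixed model will analyze learning effects with training group as between-subject and pre-post-retention as within subject factor". The SAP's Primary outcome section likewise treats the pre-test as one of three test moments. Neither document adjusts for the pre-test value or sets the two groups' pre-test means equal.

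The sample size (Protocol 5.1) is for a "repeated measures ANOVA with a within-between interaction design", pre versus post by training versus control, with no covariate term.

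**The concern.** Under randomisation a baseline difference says nothing about whether a covariate is worth adjusting for. That depends on how well it predicts the outcome, here the change in speed. A rule keyed to group difference can therefore pass over a useful covariate or admit a useless one. The pre-test, usually the strongest available predictor of the post-test, is used only as an outcome level, which fixes its weight at that of a change score.

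What is at stake is precision of the group-by-time contrast with 20 participants per group, and a covariate step that cannot be reproduced from the SAP as written.

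**Working it through.** **Inputs.** From Protocol 5.1: 20 per group; 0.0916 (SD 0.0350) m/s as reference, 0.1094 (SD 0.0418) with training, SD 0.0255 at the earlier measurement; two-sided alpha 0.05. Difference 0.1094 − 0.0916 = 0.0178. Assumed, because the documents do not give them: the pre-post correlation ρ, which SD belongs to which group and moment, the covariate's correlation r with change, and the entry threshold.

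**Stated sample size.** Pooled SD √[(0.0350² + 0.0418²)/2] = 0.03855; d = 0.0178/0.03855 = 0.462; f = d/2 = 0.231. With ρ = 0.5, λ = f²·N·m/(1 − ρ) = 0.231² × 40 × 2/0.5 = 8.53, and F(1, 38) gives 81.2% power. So N = 40 reproduces. The powers below are lower because they take the groups as equal at pre and 0.0178 apart at post; f is then d/4, which gives about 30% at ρ = 0.5 with equal SDs. That is a separate matter. Here only differences between analyses count.

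**Covariate as a main effect.** In mixed models fitted to simulated complete data at three moments, the group-by-time estimate and SE were identical with and without the covariate (for example 0.9507, SE 0.34215, both ways). The gain is nil.

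**Covariate with its time interaction.** Simulation of post minus pre, 40,000 runs per setting, ρ = 0.5, SDs 0.0255 (pre), 0.0350 (control post), 0.0418 (training post). The rule was tried with entry at p<0.05, p<0.20, 0.5 SD and 0.25 SD.

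| r with change | Never adjust | Imbalance rule | Always adjust |
|---|---|---|---|
| 0.5 | 36.5% | 36.3, 37.0, 36.4, 38.7% | 44.8% |
| 0.3 | 36.4% | 36.0–36.5% | 38.4% |
| 0 | 36.9% | 36.0–36.7% | 35.8% |

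At r = 0.5 the type I error was 5.0% never adjusting, 3.8–4.4% under the rule and 5.1% always adjusting. A repeat run at r = 0.5 gave 36.6% never, 36.6–39.2% under the rule and 45.3% always. Hence about 0 to 3 points for the rule (39.2 − 36.6 = 2.6) and about 2 to 9 for always adjusting (38.4 − 36.4 = 2.0; 45.3 − 36.6 = 8.7). With a large effect (d = 0.909), r = 0.7 and entry at p<0.20, the rule reached 86.0% against 80.3% unadjusted, nearly 6 points; always adjusting gave 97.1%.

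**Conditioning on the pre-test.** Planned: contrast variance = Σ over groups of (SD²pre + SD²post − 2ρ·SDpre·SDpost)/20, df 38. Adjusted: post on group and pre, df 37, including the factor 1 + 1/36 for estimating the slope. Worked case, first SD reading, ρ = 0.5: the planned SE is √[(0.000983 + 0.001332)/20] = 0.01076; the adjusted/planned variance ratio is 0.993. Simulated power, planned → adjusted:

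| SDs: pre / control post / training post | ρ = 0.3 | 0.5 | 0.7 | 0.9 |
|---|---|---|---|---|
| 0.0255 / 0.0350 / 0.0418 | 28.5→31.1 | 36.3→36.7 | 50.9→49.9 | 80.9→88.4 |
| 0.0350 / 0.0350 / 0.0350 | 26.2→36.8 | 34.9→43.2 | 52.5→58.3 | 93.8→94.2 |
| 0.0350 / 0.0350 / 0.0418 | 24.1→31.3 | 31.5→36.4 | 47.7→50.1 | 89.4→88.6 |

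The change runs from −1.0 to +10.6 points, with a gain in 10 of 12 cells. The two losses occur where the pre-post slope is near 1, that is, where a change score is already close to the best weighting: 0.7 × 0.0384/0.0255 = 1.05 and 0.9 × 0.0384/0.0350 = 0.99, with 0.0384 the mean of the two post SDs.

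**The case against.** Using baseline as a level of time in a mixed model is standard and unbiased. Under the SD reading closest to Protocol 5.1 the gain from conditioning on the pre-test is near nil at ρ = 0.5–0.7. The largest gain needs equal SDs and ρ = 0.3. The calculations also compare two moments, not the three-moment model proposed, and the SAP leaves the covariance structure open. With a random intercept over three moments, the planned analysis gave 34.1% where the change-score t test gave 36.7%, a shift larger than some of the gains shown. All of this stands. It limits the size of the point, not its direction.

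Four stronger readings are tempting, and the documents do not support them.

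- *Imbalance is when adjusting costs most precision.* This compares adjusted variance in imbalanced samples with unadjusted variance over all samples. Within the same imbalanced samples, the unadjusted contrast carries the imbalance. Adjusting then lowers mean squared error once r² > (1 − r²)/38, that is r > √(1/39) = 0.16. At r = 0.31 in samples triggered at p<0.05, the mean squared error was 0.141 unadjusted and 0.105 adjusted, and the type I error 10.0% and 5.1%.
- *A useful covariate is left out of most samples.* This depends on a threshold that the SAP does not state. At 0.25 SD a single covariate enters in 43% of samples, and at least one of four independent scales in 1 − 0.57⁴ = 89%.
- *Covariates will be picked to favour the result, or imbalance is the sole criterion.* The blind review is a real safeguard against outcome-driven choice, and the wording does not exclude weighing relation to outcome. It does not say how group differences would be judged while blind.
- *The Mini-BESTest will be a covariate for itself.* It is a tertiary outcome (pre and retention), and the covariate sentence covers balance skills for all outcomes, so this is possible. Nothing says that it is planned.

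**Conclusion.** The point holds as one of efficiency and pre-specification. There is no overall bias, and type I error is not inflated: it is about 3.8–4.7% under the imbalance rule at r = 0.3–0.5. The rule buys about 0 to 3 points of power over no adjustment in the N = 40 settings simulated, and up to about 6 with a liberal threshold, a strong covariate and a large effect. A covariate that predicts change, always included with its time interaction, would give about 2 to 9. Conditioning on the pre-test is worth between about −1 and just over +10 points across assumed ρ of 0.3–0.9 and three SD readings. The true value cannot be fixed from the documents, because ρ is not given. Confidence in the size is moderate. The change is worth making because it is nearly free.

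**What to change.** In the SAP, Main analysis, remove selection of covariates by between-group difference and specify instead:

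- A linear mixed model on pre, post and retention, with a common pre-test mean for both groups, unstructured covariance, a small-sample degrees-of-freedom correction, and group-by-time terms at post and retention always retained, whatever the fitting criteria say. Within-group changes remain estimable.
- For the Mini-BESTest, measured only at pre and retention, a comparison of groups at retention adjusted for the day-1 score, with that score not entered again.
- Optionally, any further cognitive or balance covariate named in advance for its expected relation to change, included whatever the imbalance, and entered with its time interaction.

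The cost is SAP wording; all variables are already collected. The downside is up to about 1 point of power where the pre-post slope is near 1, and about 1 point for each uninformative covariate (36.9% to 35.8% for one; 37.0% to 35.3% for two). Further covariates are therefore a trade-off, not a requirement.

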Recent systematic reviews showed that postural control in older adults can be improved with training¹⁵. However, little is known about the ability and maintenance of re-learning to weight-shift, let alone about its underlying mechanism. Therefore, the primary aim of this project will address this lacuna by studying the effects of training in weight-shifting performance in older adults and its underlying neural imprint. As our previous study (unpublished) showed that adding an extra cognitive task in a so-called dual-task (DT) negatively affects weight-shifting performance, a secondary aim will be to test whether weight-shift training will enhance performance during such DT conditions. The results of this study might form a basis for future technology-based rehabilitation programs.

4 Study objectives

The effects of postural learning on cortical activity have not been identified yet in older adults. During non-postural tasks, older adults needed greater activity and recruited more brain areas during automatization compared to young adults. This is suggested to be the primary reason for impaired motor automaticity with age¹⁶. We will use fNIRS to examine postural learning in the upright position for the first time in older adults. More specifically, we will investigate:

1. Changes in brain activity in frontal, (pre-)motor, and parietal regions associated with the acquisition and consolidation of weight shifting in older adults. In addition, as moving the Centre of Mass (CoM) deliberately also loads sensorimotor function, we will include the parietal cortex as region of interest.
2. Changes in brain activity in frontal, (pre-)motor, and parietal regions associated with the acquisition and consolidation of weight shifting compared to no training (control group).
3. Changes in brain activity in frontal, (pre-)motor, and parietal regions associated with the transfer of single-task acquisition and consolidation of weight shifting to dual-task weight shifting performance.

5 Methodology of the research

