### **Tertiary outcomes:**

## 1. Clinical balance outcome

The MiniBEST will be administered to assess general balance. The scale consist of 4 subscales: 1) anticipatory postural control; 2) reactive postural control; 3) sensory orientation; 4) dynamic gait. Total score (range 0-28) will be compared between the two days (pre, retention) and between the two groups (training, control).

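### Bonferroni for the post-hoc contrasts is valid, but Holm within a named family controls the same error rate with somewhat more power

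*SAP*

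**What the plan says.** The SAP's Main analysis says that all outcomes will be "compared between training and control group and pre, post and retention test using linear mixed models", and then: "Post-hoc testing will be corrected for multiple testing by Bonferroni corrections". It does not say which contrasts are post-hoc, how many there are, whether they are within or between groups, or whether the interaction must be significant first.

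The primary outcome, mediolateral speed, is "compared between the three test moments (pre, post, retention) and between the two groups (training, control) during the Wasp Game ST and DT". The Mini-BESTest has only two time points: "Total score (range 0-28) will be compared between the two days (pre, retention".

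In Protocol Section 4, Objective 2 concerns changes in brain activity "associated with the acquisition and consolidation of weight shifting compared to no training (control group"). Objective 1 asks about acquisition and consolidation without reference to controls. Neither is tied to a named contrast.

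The sample size (Protocol 5.1) covers two moments only ("within: pre vs post: between: training vs control") and makes no allowance for multiple contrasts.

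**The concern.** With two groups and three moments, the group-by-moment interaction has 2 degrees of freedom. A significant result says that the groups changed differently somewhere, but not whether the difference arose at post-test, at retention or at both. The follow-up contrasts answer that, so the multiplicity rule for them bears directly on the trial's questions.

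Bonferroni tests each of three contrasts at 0.05/3 = 0.0167 whatever the others show. Holm gives the same family-wise guarantee with less strict later steps. In a trial of 20 per arm, power given up without any gain in error control is worth recovering if that costs one sentence.

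**Working it through.** **Inputs.** Protocol 5.1 gives speed after practice of 0.0916 (SD 0.0350) m/s in the sponsor's previous study, expected speed after training of 0.1094 (SD 0.0418) m/s, 20 per group, alpha 0.05 and power 80%. Assumptions: two-sided tests, equal correlation ρ between moments, and a training gain fully retained at 24 hours. The documents do not state ρ, so a range is shown.

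**The plan's own figure.** Difference = 0.1094 − 0.0916 = 0.0178 m/s. Pooled SD = √[(0.0350² + 0.0418²)/2] = 0.03855, so d = 0.462. With f = d/2 = 0.231, ρ = 0.5 and noncentrality f²·N·2/(1 − ρ), power at N = 40 is 0.81. The stated 40 is therefore reproduced on these assumptions.

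**Power of one between-group difference in change, unadjusted.** The SD of a change is 0.03855·√[2(1 − ρ)], and the noncentrality of the t test (38 df) is 0.0178·√(20/2) divided by that SD.
- ρ = 0.5: noncentrality 1.46, power 30%
- ρ = 0.7: noncentrality 1.89, power 45%
- ρ = 0.87: noncentrality 2.86, power 80%

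For this contrast, 80% therefore needs ρ near 0.87. The gap from the planned 80% at ρ = 0.5 comes from f = d/2, where a difference in change corresponds to f = d/4. That is a separate sample-size matter.

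**Why Holm loses nothing.** Holm compares the ordered p-values with 0.05/3, 0.05/2 and 0.05 and stops at the first failure. The first step is Bonferroni's and the later ones are easier. So every Bonferroni rejection is also a Holm rejection, under the same conditions.

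**Why a closed test is available.** The post-retention difference equals the pre-retention difference minus the pre-post difference. If any two of the three are zero, so is the third. Every joint null hypothesis is then the 2-df interaction null. If that is rejected at 0.05, each contrast can be tested at the full 0.05 with strong control.

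**Simulation.** 20 per arm, three between-group change contrasts, t tests on changes, Hotelling test for the 2-df interaction, 100,000 runs per setting. Percentages are Bonferroni / Holm / closed.

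| ρ | Acquisition (pre-post) | Both acquisition and retention | At least one contrast (Bonferroni = Holm) |
|---|---|---|---|
| 0.5 | 16 / 17 / 21 | 6 / 8 / 14 | 27 |
| 0.7 | 28 / 30–31 / 36 | 14 / 18 / 27 | 43 |
| 0.87 | 64 / 68 / 74 | 48 / 56 / 67 | 80 |

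A separate calculation that tests the interaction with a 2-df F test gives acquisition power one to two points higher (17/18/22, 29/31/37 and 66/70/76), with the same ordering.

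**Error control.** Under the global null, family-wise error is about 4.3–4.4% for Bonferroni and Holm and 4.9–5.0% for the closed test. At ρ = 0.87, with post = retention the only true null, it is 1.7%, 3.3% and 5.0%. None exceeds 5%.

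**A cost of the closed test.** With 38 df, Bonferroni needs t² > 6.27 while the 2-df test needs T² > 6.68. A lone contrast can pass the former and be stopped by the latter. That happened in about 0.5 to 1% of simulated trials over these correlations.

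**The case against.** Bonferroni is valid, pre-specified and conservative, and it yields simple simultaneous intervals. All of that stands: the choice cannot produce a false claim at more than the nominal rate.

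The family is also not in the documents. Three between-group contrasts are a reasonable reading, but within-group follow-ups are equally open, given Objective 1. For the within-training pre-post change (0.0668 to 0.1094 m/s, ρ = 0.5) the loss is trivial: power is 0.999 at 0.05 and 0.992 at 0.05/3. This also stands, and it is why the fix must name the family as well as change the method.

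Three stronger readings are tempting but not supported:
- A reader might infer that all 15 pairs of the six group-by-moment cells would be tested at 0.05/15. Nothing in either document points to that family.
- A reader might take the gains seen when each contrast starts at 80% power as the trial's own. On the Protocol's figures that needs ρ near 0.87, which no document states. At 0.5, Holm adds one to two points.
- A reader might expect Holm to make a positive finding more likely. It leaves the chance of at least one rejection unchanged. Its benefit is in the second and later contrasts, and the SAP does not require both acquisition and retention to be shown.

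Nor is the closed test better without qualification. It can stop a contrast that Bonferroni would reject. It is also valid only within one set of three contrasts: if one significant interaction licensed unadjusted tests across all cells, three flat control-group contrasts would carry a family-wise error of about 12%.

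**Conclusion.** The point holds as one of efficiency. Bonferroni is sound but less powerful than Holm at the same family-wise error, and that ordering needs no assumption about effect size.

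The size of the gain does need assumptions. With full retention and equal correlations, for ρ from 0.5 to 0.87, Holm adds about 1 to 4 points per contrast and 2 to 8 for showing both. The closed test adds about 5 to 10 and 8 to 19. At the lower correlations power is poor under every method, and no multiplicity rule repairs that. These figures concern speed only; the documents give no variability for the fNIRS outcomes.

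This is a cheap improvement, not the correction of an error. The undefined family deserves at least as much attention as the choice of method.

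**What to change.** Replace the SAP sentence on post-hoc testing with wording to this effect:

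> Post-hoc tests use the Holm procedure at family-wise 0.05. For each outcome measured at three moments, and separately for each task condition (ST, DT) where both apply, the family is the three between-group differences in change: pre-post, pre-retention and post-retention. Within-group follow-ups form their own Holm family. The Mini-BESTest has one between-group change contrast and needs no correction.

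Optionally, for the three between-group contrasts only, specify the closed test: the 2-df interaction at 0.05 within that outcome and condition, then each contrast at 0.05. The SAP must then state that the group-by-moment interaction always stays in the model, because the current text lets fitting criteria choose the model.

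The cost is one paragraph of SAP text and no new data. Holm and the closed test have no simple matching simultaneous intervals, so report unadjusted intervals beside the adjusted decisions. The closed test also carries the small risk, shown above, of stopping a contrast that Bonferroni would reject.
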